8.1.6 Interim Analyses and Data Monitoring

No interim analysis or data monitoring is planned for this study.

8.1.7 Multicenter Studies

The clinical study will be conducted under a common protocol for each investigational site with the intention of pooling the data for analysis. Every effort will be made to promote consistency in study execution at each investigational site. The study is intended to be conducted in a manner such that a minimum of 15 subjects will be randomized and included in the ITT population (i.e., at least ten subjects in the active treatment arm and five subjects in the vehicle treatment arm) for any investigator. In the event that there are too few subjects in a treatment arm for an

investigational site, then the site's data will be combined with other site's data to achieve the desired sample size minimum per treatment arm. The combining of investigator data will be accomplished by taking the data of the investigator with the smallest enrollment and combining them with the data of the investigator with the largest enrollment, restricted to investigational sites which did not meet minimum enrollment. If there is a further need to combine data, then the data of the investigator with the second smallest enrollment will be combined with the site's data which had the second largest enrollment (restricted to investigational sites which did not meet minimum enrollment), and so on. This process will continue for all investigators who did not have a minimum of 15 subjects enrolled. The process of combining investigator data that have insufficient subjects per treatment arm will result in redefining the groups of investigators for the purposes of statistical analyses. These combined groups will be referred to as "analysis centers" in the statistical analyses.

The consistency of treatment response will be investigated across the analysis centers subsequent to combining the data as described above. Statistical tests will be conducted to identify if there are extreme analysis centers that could affect the interpretation of common statistical and clinical conclusions. An analysis center by treatment interaction will be included in the primary analyses to test for parallel treatment effect at an alpha level of 0.10. Change from Baseline in inflammatory and non-inflammatory lesions will be analyzed with an ANCOVA (unranked or ranked) with factors of treatment group, analysis center and treatment group by analysis center interaction and the respective Baseline lesion count variable as a covariate. For the purpose of testing consistency of treatment response, the dichotomized IGA will be analyzed with a logistic regression with factors of treatment group, analysis center, and the interaction term of treatment group by analysis center. Further examination will follow for any variables that have a significant ANCOVA or logistic regression interaction term.

In the event that the ANCOVA or logistic regression interaction (referred to henceforth as the "appropriate test") p-value is less than or equal to 0.10, a sensitivity analysis that excludes analysis centers with the extreme efficacy result will be performed to determine the robustness of the treatment effect. On the other hand, if all three analyses result in interaction terms with p-values greater than 0.10, then the conclusions from the pooled data will be considered to be free of the impact of extreme analysis centers.

The first step in conducting a sensitivity analysis is to identify the extreme analysis center or centers that contribute to the statistical significance of the appropriate test. The process involves submitting subsets of analysis centers to the appropriate test and observing the appropriate test p-value for the subset. Subsets with p-values greater than 0.10 for the appropriate test are considered homogeneous.

The search for an extreme analysis center begins by analyzing all subsets that can be created by excluding one analysis center. If one or more of the subsets result in an appropriate test p-value greater than or equal to 0.10, then the analysis center excluded from the subset with the largest p-value for the appropriate test is deemed to be the extreme analysis center.

If all appropriate test subset p-values are less than or equal to 0.10, then the process will analyze the appropriate test for all subsets that can be created by excluding two analysis centers. If one or more of these subsets generate appropriate test p-values larger than 0.10, then the analysis centers excluded from the subset with the largest appropriate test p-value are deemed the extreme analysis centers.

Thus, the process of identifying the extreme analysis centers will continue in a stepwise manner by first excluding one, then two, then three, etc., analysis centers until the appropriate test p-value exceeds 0.10.

Once the extreme analysis center or centers have been identified, then the treatment p-values of the remaining analysis centers will be computed. Inferences will be drawn from the treatment p-value, as well as any pertinent observations regarding the extreme analysis center or centers. Additionally, it is noted that this process excludes patients from the analysis in a non-random manner and has an unpredictable impact on the power of the treatment effect test. In the event that the treatment effect of the remaining subset is not statistically significant, due consideration of the post-hoc aspects of the process will be given when the results are interpreted. Conclusions will be presented by the Sponsor as appropriate to the findings of the sensitivity analysis.

Prior to investigating the treatment effect within the analysis centers, the treatment effect within investigational site will be investigated to determine if the site-to-site variability is such that it could mask the analysis center effects. Thus, prior to pooling, change from Baseline in inflammatory and non-inflammatory lesions will be analyzed with an ANCOVA (unranked or ranked) with factors of treatment group, investigational site, and treatment group by investigational site interaction, and the respective Baseline lesion count variable as a covariate. The dichotomized primary endpoint will be analyzed with a logistic regression with factors of treatment group, investigational site, and the interaction term of treatment group by investigational site. If any of the analyses are not computationally feasible due to some investigational sites having very few subjects enrolled, the low-enrolling investigational sites will be excluded from the analysis.

8.1.8 Multiple Comparisons/Multiplicity

The overall Type I error will be controlled by requiring the three co-primary efficacy endpoints to be statistically significant. Specifically, failure of either one of the primary efficacy endpoints will invalidate the statistical significance of the secondary efficacy endpoints.

Evaluation of the secondary efficacy variables will use a gated sequential procedure starting with the comparisons of the first step and proceeding onto the next step and etc.

A stepwise process will be conducted for testing the secondary efficacy endpoints in order to control for multiplicity. These tests will be performed for only the ITT population. The testing process will terminate whenever a statistical test for a step is not significant. All subsequent tests for the remaining steps will be considered not significant. The order of testing is provided below.

Step Number	Secondary Endpoint
1	Percent change from Baseline, in non-inflammatory lesion count at Week 12.
2	Percent change from Baseline, in inflammatory lesion count at Week 12.
3	Proportion of patients in the E-BPO/E-ATRA cream arm compared to vehicle control achieving at least a 4-point reduction on Item 1 (pimples) of the PREFACE from Baseline to Week 12.
4	Proportion of patients in the E-BPO/E-ATRA Cream arm compared to vehicle control achieving at least a 4-point reduction on Item 5 (embarrassment) of the PRE-FACE from Baseline to Week 12.
5	Absolute change from Baseline, in non-inflammatory lesion count at Week 8
6	Absolute change from Baseline, in inflammatory lesion count at Week 8.
7	Absolute change from Baseline, in non-inflammatory lesion count at Week 4..

8.1.9 Use of an Efficacy Subset of Subjects

Subjects randomized to study drug who were dispensed study product and do not have major protocol deviations will form the PP Population. The requirements for the PP Population are outlined in Section 8.4.4. Any additional major protocol deviations will be defined at the time of evaluability evaluation, the time between the database soft lock and hard lock before unblinding.

Excluding subjects who have major protocol deviations will decrease the variability in treatment response and will allow for a better determination of dose-response relationship of S6G5T-3.

8.1.10 Active-Control Studies Intended to Show Equivalence

Not applicable to this study.

8.1.11 Examination of Subgroups

Subset analyses will be conducted for the ITT populations for the subgroups based on at least the following:

- Baseline Global Severity;
 - Categorized as Baseline IGA = 3 (moderate) and Baseline IGA = 4 (severe); due to the inclusion criteria requiring subjects to have either a 3 or 4 IGA score at study entry other IGA response categories will not be presented
- Sex;
 - Male versus female subjects
- Age;
 - Dichotomized to less than the median age of ITT subjects and greater than or equal to the median age of ITT subjects
 - Categories of less than 18, 18 to less than the median age of ITT subjects and greater than or equal to the median age of ITT subjects; if the median age of ITT subjects is 18 or less, the subgroup will be less than 18 and greater than or equal to 18
 - Categories of 9-11 years, 12-17 years, 18-30 years, and 31 years and older
- Ethnicity;
 - Categorized as Hispanic or Latino and Not Hispanic or Latino; ethnicities of Not Reported and Unknown will not be included
- Race
 - Categorized as White and Non-White; subjects indicating more than one race category which includes both white and a non-white race will be summarized under the Non-White subgroup.

Subset analyses will be conducted on the variables absolute change from Baseline in inflammatory lesions at Week 12 as well as the dichotomized global severity score at Week 12. These analyses will contain only descriptive statistics.

8.2 Disposition of Subjects

The number of subjects included in each analysis population (randomized, ITT, Safety, and PP) will be summarized by treatment group and overall. The number of subjects completed and discontinued (including the reasons for discontinuation) will be summarized for each treatment group as well as by overall. The percentages will be calculated based on the number of randomized patients, unless otherwise specified.

8.3 Protocol Deviations

In order to define the PP Population, protocol deviations potentially influencing the evaluation of the primary efficacy endpoint will be defined as major deviations. The protocol deviations that will exclude a subject from PP are given in Section 8.4.4.

In case other deviations detected during the study conduct are considered to potentially influence the evaluation of the primary efficacy endpoint, these deviations will be documented prior to the database lock and the patients having these deviations will be excluded from the PP Population.

All protocol deviations will be reported to the sponsor and recorded throughout the study. Protocol deviations will not be entered into the database. SolGel will provide a list of protocol deviations to QST. A tabulation of protocol deviations will be presented in a data listing.

8.4 Data Sets Analyzed

Subjects will be presented/summarized based on the primary reason for exclusion. Below is the order to be used in summaries:

8.4.1 Randomized Population

All subjects who are randomized to study treatment will be included in the randomized population and will be analyzed according to the treatment group they were randomized. Listings will be provided for all randomized subjects.

8.4.2 Intent-to-Treat (ITT) Population

All subjects in the randomized population who are dispensed study product will be included in the ITT population and will be analyzed according to the treatment group they were randomized. All efficacy analyses will be presented using the ITT population.

8.4.3 Safety Population

All subjects in the randomized population who are presumed to have used the study product at least once and who provide at least one post-baseline safety evaluation will be included in the Safety population and will be analyzed according to the treatment they received. Presumed to have used study product will be defined as having at least one confirmed application of study medication. All safety analyses will be performed using the Safety population.

8.4.4 Per-Protocol (PP) Population

All subjects in the ITT population who complete the Week 12 evaluation without any significant protocol violations will be included in the PP population and analyzed according to the treatment group they received. The PP population will include subjects in the ITT population who do not meet any of the following criteria:

- Failed any of the inclusion/exclusion criteria;
- Have taken any interfering concomitant medications;
- Did not attend the Week 12 Visit;
- Missed more than 1 post-baseline study visit prior to Week 12;
- Have not been compliant with the dosing regimen (i.e., Patients may not miss more than five consecutive days of applications and must take 80-120% of expected applications. The number of expected applications will be determined for each Patient based on the length of their participation in the study);
- Out of visit window (+/- 4 days) at the 12-week Visit.

Subjects that discontinue from the study due to an AE related to study treatment or documented lack of treatment effect will be included in the PP population. Data for these subjects will not be imputed by multiple imputation but rather their data will be imputed with values consistent with their status as treatment failures. See Section 8.1.5 for additional detail. Prior to breaking the blind, other additional criteria may be added to the list to accommodate for unforeseen events that may occur during the conduct of the trial and result in noteworthy study protocol violations.

All efficacy analyses performed on the PP population will be according to the treatment they received.

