12.2 Screen Failure and Discontinuation Criteria

A screen failure is a Patient who is not randomized/enrolled in the study due to ineligibility, after signing an ICF, and would not have received study product. The ICF signed by the Patient should be kept with the source document for Patients who do not pass the screening procedures. The documentation should include identification of the eligibility criterion or criteria that were and were not met. The Patient should not be re-screened for this study without Sol-Gel or designee's approval.

Although encouraged to complete the study whenever possible, Patients are free to discontinue their participation in this study at any time and for any reason without prejudice. A Patient may be withdrawn from the study prior to study completion for any of the following reasons:

- Investigator opinion that it is not in the Patient's best interest to continue.
- Patient Request/Withdraw Consent – Whenever the Patient decides it is in his/her best interest to withdraw.
- Lack of Efficacy/Worsening of Condition.
- AE – when the Investigator thinks it's in the Patient's best interest
- Lost to Follow-up – Documentation confirmed at minimum by two phone calls and certified letter. Best efforts should be performed to capture an explanation for the lost-to follow-up event.
- Protocol Violation – When requirements of the protocol are not respected, especially when Patient safety is concerned.
- Pregnancy.

Study staff should make efforts to encourage Patients to complete the study on time. If a Patient prematurely withdraws during the study, every effort should be made to complete at least the Week 12/ End of Study or Early Termination assessments.

In the case of Patients who discontinue due to an AE, the Investigator will conduct follow-up contacts with the Patient until the Investigator, Sponsor and Medical Monitor agree the event is satisfactorily resolved and/or stabilized.

Patients discontinued early from the study shall not be replaced.

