17.1.4 Analysis Populations

Approximately 420 male and female Patients at least 9 years of age with moderate or severe acne vulgaris with 3 or 4 [moderate to severe] on the IGA scale will be enrolled and randomized in the study with a 2:1 randomization ratio, it is anticipated that:

- 280 Patients will be randomized to receive S6G5T-3, Encapsulated Benzoyl Peroxide 3%/Encapsulated All-Trans-Retinoic Acid 0.1% Cream
- 140 Patients will be randomized to receive S6G5T-8, Vehicle Cream

The ITT population will consist of all randomized Patients who were dispensed study product. The safety population will be comprised of all randomized Patients who are presumed to have used the study product at least once and who provide at least one post-baseline safety evaluation.

An intent-to-treat (ITT) analysis will be conducted. A per-protocol (PP) analysis will also be conducted. Patients will be eligible for the PP analysis if they complete the 12-week evaluation without noteworthy study protocol violations (i.e., any Patient or Investigator activity that could have possibly interfered with the therapeutic administration of the treatment or the precise evaluation of treatment efficacy). The PP population will include Patients in the ITT population who do not meet any of the following criteria:

- Failed any of the inclusion/exclusion criteria;
- Have taken any interfering concomitant medications;
- Did not attend the Week 12 Visit;
- Missed more than 1 post baseline study visit prior to Week 12;

- Have not been compliant with the dosing regimen (i.e., Patients may not miss more than five consecutive days of dosing and must take 80-120% of expected doses. The number of expected doses will be determined for each Patient based on the length of their participation in the study);
- Out of visit window (± 4 days) at the 12-week Visit.

Patients that discontinue from the study due to an AE related to study treatment or documented lack of treatment effect will be included in the PP population. Data for these Patients will not be imputed by multiple imputation but rather their data will be imputed with values consistent with their status as treatment failures. Prior to breaking the blind, other additional criteria may be added to the list to accommodate for unforeseen events that occurred during the conduct of the trial that result in noteworthy study protocol violations.

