8.8 Safety Evaluation

8.8.1 Extent of Exposure

The extent of exposure to study drug in each treatment group will be summarized by total number of days of exposure, total number of applications, number of missed applications and number and percentage of subjects who are compliant. A subject will be considered compliant with the dosing regimen if the subject applied 80% to 120% of the expected number of applications and did not miss more than 5 consecutive applications while enrolled in the study.

Days of exposure = Date of last study application – Date of first study application + 1

The total number of applications taken is as follows:

(Date of Last Application – Date of First Application + 1) – (Number of Days marked as missed applications on the CRF) + (Number of extra applications marked on the CRF)

If a subject did apply medication on the last day, the total number of applications expected is as follows:

Date Subject End Participation – Date of Baseline +1.

If the total number of applications exceeds 89 then it will be set to 89.

If a subject did not apply medication on the last day, the total number of applications expected is as follows:

Date Subject End Participation - Date of Baseline

If the total number of applications exceeds 88 then it will be set to 88.

Compliance will be calculated as a percentage as 100 times the total number of applications taken from the first application until Week 12 divided by the total number of applications expected from first application until Week 12. Subjects who discontinue study medication before Week 12 will be considered to be 0% compliant for the number of days from discontinuing study medication until Week 12.

Compliance will not be calculated for subjects who are lost to follow-up or subjects who have unknown first or last application dates.

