Table 14.3.1.2.1: Summary of Treatment-Emergent Adverse Event Characteristics (Safety Population).....	152
Table 14.3.1.2.2: Summary of Treatment-Emergent Adverse Events by MedDRA System Organ Class and Preferred Term (Safety Population).....	154
Table 14.3.1.2.3: Summary of Treatment-Emergent Adverse Events by Severity (Safety Population)	155
Table 14.3.1.2.4: Summary of Treatment-Emergent Adverse Events by Relationship to Study Drug (Safety Population)	156
Table 14.3.1.3.1: Summary of Treatment-Emergent Serious Adverse Event Characteristics (Safety Population).....	157
Table 14.3.1.3.2: Summary of Treatment-Emergent Serious Adverse Events by MedDRA System Organ Class and Preferred Term (Safety Population).....	159
Table 14.3.1.3.3: Summary of Serious Treatment-Emergent Adverse Events by Severity (Safety Population)	160
Table 14.3.1.3.4: Summary of Treatment-Emergent Serious Adverse Events by Relationship to Study Drug (Safety Population).....	161
Table 14.3.1.4: Summary of Vital Signs (Safety Population)	162
Table 14.3.1.4.2: Shift Table of Vital Signs (Safety Population).....	167
Table 14.3.1.5: Summary of Abnormal Physical Examination Findings by Visit (Safety Population)	168
Table 14.3.1.6: Summary of Patient Global Impression of Treatment Side-Effects (PGI-SE) at Each Evaluation (Safety Population).....	169

Table 14.0.1: Summary of Subject Completion/Discontinuation
(All Randomized Subjects)

	E-BPO/E-ATRA 3%/0.1% Cream (N= xxx)	Vehicle Cream (N=xxx)	Total (N=xxx)
Completed Study			
Yes	xx (xx.x%)	xx (xx.x%)	xx (xx.x%)
No	xx (xx.x%)	xx (xx.x%)	xx (xx.x%)
Reason for Discontinuation			
Adverse Event	xx (xx.x%)	xx (xx.x%)	xx (xx.x%)
Lost to Follow-Up	xx (xx.x%)	xx (xx.x%)	xx (xx.x%)
Lack of Efficacy	xx (xx.x%)	xx (xx.x%)	xx (xx.x%)
Pregnancy	xx (xx.x%)	xx (xx.x%)	xx (xx.x%)
Protocol Violation	xx (xx.x%)	xx (xx.x%)	xx (xx.x%)
Withdrawal by Parent/Guardian	xx (xx.x%)	xx (xx.x%)	xx (xx.x%)
Withdrawal by Subject	xx (xx.x%)	xx (xx.x%)	xx (xx.x%)
Study Terminated by Sponsor	xx (xx.x%)	xx (xx.x%)	xx (xx.x%)
Physician Decision	xx (xx.x%)	xx (xx.x%)	xx (xx.x%)
Worsening of Condition	xx (xx.x%)	xx (xx.x%)	xx (xx.x%)
Other	xx (xx.x%)	xx (xx.x%)	xx (xx.x%)

SOURCE: USERNAME\SPONSOR\PROJECT\JOBNAME (DATE, TIME)

Table 14.0.2.1: Summary of Subject Enrollment and Evaluability
(All Randomized Subjects)

	E-BPO/E-ATRA 3%/0.1% Cream (N=xxx)	Vehicle Cream (N=xxx)	Total (N=xxx)
Number of Randomized Subjects	xx	xx	xx

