(Page 13 of 14)

Stinging	E-BPO/E-ATRA 3%/0.1% Cream (N=xxx)	Vehicle Cream (N=xxx)
Baseline		
n	xx	xx
0 – None	xx (xx.x%)	xx (xx.x%)
1 – Mild	xx (xx.x%)	xx (xx.x%)
2 – Moderate	xx (xx.x%)	xx (xx.x%)
3 – Severe	xx (xx.x%)	xx (xx.x%)
Week 2		
n	xx	xx
0 – None	xx (xx.x%)	xx (xx.x%)
1 – Mild	xx (xx.x%)	xx (xx.x%)
2 – Moderate	xx (xx.x%)	xx (xx.x%)
3 – Severe	xx (xx.x%)	xx (xx.x%)
Week 4		
n	xx	xx
0 – None	xx (xx.x%)	xx (xx.x%)
1 – Mild	xx (xx.x%)	xx (xx.x%)
2 – Moderate	xx (xx.x%)	xx (xx.x%)
3 – Severe	xx (xx.x%)	xx (xx.x%)

Note: No imputation of missing data.

SOURCE: USERNAME\SPONSOR\PROJECT\JOBNAME (DATE,TIME)

Table 14.3.1.1: Summary of Cutaneous Signs and Local Tolerability at Each Evaluation
(Safety Population)
(Page 14 of 14)

Stinging	E-BPO/E-ATRA 3%/0.1% Cream (N=xxx)	Vehicle Cream (N=xxx)
Week 8		
n	xx	xx
0 – None	xx (xx.x%)	xx (xx.x%)
1 – Mild	xx (xx.x%)	xx (xx.x%)
2 – Moderate	xx (xx.x%)	xx (xx.x%)
3 – Severe	xx (xx.x%)	xx (xx.x%)
Week 12		
n	xx	xx
0 – None	xx (xx.x%)	xx (xx.x%)
1 – Mild	xx (xx.x%)	xx (xx.x%)
2 – Moderate	xx (xx.x%)	xx (xx.x%)
3 – Severe	xx (xx.x%)	xx (xx.x%)

Note: No imputation of missing data.

SOURCE: USERNAME\SPONSOR\PROJECT\JOBNAME (DATE,TIME)

Table 14.3.1.2.1: Summary of Treatment-Emergent Adverse Event Characteristics
(Safety Population)
(Page 1 of 2)

	E-BPO/E-ATRA 3%/0.1% Cream (N=xxx)	Vehicle Cream (N=xxx)
Subjects Reporting Any Treatment-Emergent Adverse Event	xx (xx.x%)	xx (xx.x%)
Number of Treatment-Emergent Adverse Events	xx	xx
Subjects Reporting Any Serious Treatment-Emergent Adverse Event	xx (xx.x%)	xx (xx.x%)
Number of Serious Treatment-Emergent Adverse Events	xx	xx
Subjects Reporting Treatment-Emergent Adverse Event with Outcome of Fatal	xx (xx.x%)	xx (xx.x%)
Number of Treatment-Emergent Adverse Events with Outcome of Fatal	xx	xx
Subjects Who Discontinued Study Drug Due to a Treatment-Emergent Adverse Event	xx (xx.x%)	xx (xx.x%)
Number of Treatment-Emergent Adverse Events Leading to Discontinuation of Study Drug	xx	xx
Subjects Who Discontinued from the Study Due to a Treatment-Emergent Adverse Event	xx (xx.x%)	xx (xx.x%)
Number of Treatment-Emergent Adverse Events Leading to Discontinuation of Study	xx	xx

Note: Treatment-emergent adverse events are those events that were not indicated as occurring prior to first application.
Related defined as “Definitely”, “Probably”, or “Possible”. Not Related defined as “Unlikely” or “Not related”.

SOURCE: USERNAME\SPONSOR\PROJECT\JOBNAME (DATE, TIME)

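### The per-protocol treatment-failure exception applies only to patients who leave the study; one who stops the product for the same related AE but attends Week 12 is excluded for non-compliance

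*SAP*

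**What the plan says.** **The exception.** SAP 8.4.4 lists the PP exclusions (eligibility failures, interfering medication, Week 12 not attended or out of window, missed visits, non-compliance) and then carves out treatment failures: "Subjects that discontinue from the study due to an AE related to study treatment or documented lack of treatment effect will be included". Protocol 17.1.4 has the same rule: patients who discontinue from the study for a related AE or "documented lack of treatment effect will be included in the PP population". SAP 8.1.5 repeats it and fixes the score: lesion counts and IGA are set to Baseline, so change is zero.

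**The compliance criterion.** In SAP 8.4.4, "Patients may not miss more than five consecutive days of applications and must take 80-120% of expected applications". SAP 8.8.1 adds, for the days from stopping until Week 12, "Subjects who discontinue study medication before Week 12 will be considered to be 0% compliant".

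**Stopping product and leaving the study are separate events.** SAP Table 14.3.1.2.1 has a row "Subjects Who Discontinued Study Drug Due to a Treatment-Emergent Adverse Event" and a different row for leaving the study because of a TEAE. Protocol 15.1 likewise records withdrawal of the drug and withdrawal from the study in different fields.

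**Severe related AEs.** Protocol 15.5 says these patients are discontinued from the study, which brings them inside the exception.

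**Lack of effect.** Protocol 12.2 has one combined withdrawal reason, "Lack of Efficacy/Worsening of Condition". SAP Table 14.0.1 has a Lack of Efficacy row and, separately, a row "Worsening of Condition". Neither document says which of these the exception's lack-of-effect phrase refers to.

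**The concern.** The exception exists because stopping for a related AE, or for lack of effect, is a result of treatment. Deleting such patients would select PP on outcome. The plan applies that reasoning to the patient who leaves and withholds it from the patient who stops the same product for the same reason but keeps attending. The leaver stays in PP with an imputed zero change. The stayer, whose Week 12 assessment was actually made, is dropped.

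PP membership then depends partly on whether a failing patient went on attending visits. If such stops are more frequent in one arm, the supportive PP results favour that arm. PP carries the supportive analyses of the primary and secondary endpoints (SAP 8.7), so a reader will use it to judge the consistency of the ITT result.

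**Working it through.** The plan states no figure for this point. The check applies the plan's own rules to one patient and then illustrates the possible size.

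**1. Does the compliance rule remove the stayer?** SAP 8.8.1 gives the denominator: "If a subject did not apply medication on the last day, the total number of applications expected is as follows" end of participation minus Baseline, capped at 88. Take a Week 12 visit on Day 85, Baseline on Day 1, first application on Day 1, no earlier missed days, and last application on Day L.

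- Expected applications: 85 − 1 = 84.
- Applications taken: L. Consecutive missed days: 84 − L.
- Five-day rule: 84 − L ≤ 5 requires L ≥ 79. At L = 78 the run is 6 days and the patient is excluded.
- 80% rule: 0.80 × 84 = 67.2, so at least 68 applications and L ≥ 68.

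The five-day rule binds first. At the edges of the visit window the limit is L ≥ 75 for a Day 81 visit (80 − 5) and L ≥ 83 for a Day 89 visit (88 − 5). If someone argued that the five-day rule ends with the last application, the 80% rule would still exclude anyone whose last application was before Day 68 (Day 85 visit).

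**2. Two patients with the same related, non-severe AE and last application on Day 30.**

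| | Leaves the study | Stops product, attends Week 12 |
|---|---|---|
| Covered by the exception | Yes | No |
| Compliance | Overridden by the exception | 30/84 = 35.7%, with 84 − 30 = 54 consecutive missed days |
| In PP | Yes | No |
| Week 12 value | Imputed, zero change | Observed, not used in PP |

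**3. Illustrative size.** The documents give no rate of product-stoppers who stay. Assumptions: 2-5% of 280 active patients (0.02 × 280 = 5.6, about 6; 0.05 × 280 = 14), all IGA non-successes, none on vehicle, and 225 other active PP patients with the planned success rate of 33.3% (75 successes).

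- Excluded: 75/225 = 33.33%.
- 6 included: 75/231 = 32.47%, lower by 0.87 points.
- 14 included: 75/239 = 31.38%, lower by 1.95 points.

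The planned difference from vehicle is 33.3 − 12.6 = 20.7 points.

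For inflammatory lesions, treat the same shares (2% or 5%) as a fraction of the active arm with zero change. The planned difference is −16.7 − (−12.2) = −4.5. Including these patients gives 0.98 × (−16.7) + 12.2 = −4.17, or 0.95 × (−16.7) + 12.2 = −3.665.

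**The case against.** **Excluding non-adherent patients is what PP is for.** A patient weeks off product is the usual case, and the observed value stays in ITT. This would settle the matter if the plan applied compliance to everyone. It does not: it already overrides compliance and attendance for leavers with a related AE. Treating the equivalent patient alike is a matter of consistency.

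**Few patients may be affected.** This stands in part. Severe related AEs lead to study discontinuation, stops in about the last five days do not exclude, and protocol 12.2 describes withdrawal with early-termination assessments and no off-product schedule. The table rows are empty shells and predict no numbers. They do show, with protocol 15.1 and 15.5, that stopping product is treated as a distinct event.

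**Existing text might cure it.** SAP 8.4.4 allows criteria to be added before unblinding, but for protocol violations, which means more exclusions. The shell of Listing 16.2.3 has an exceptions column, but no rule extends the exception.

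**Stronger readings that the documents do not support.**

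- A reader might infer that patients withdrawn for worsening are deleted from PP. Nothing says so. The exception uses a descriptive phrase, not a disposition code, and protocol 12.2 joins worsening with lack of efficacy. The term is undefined, and that is all that can be said.
- A reader might infer that the gap must favour the active arm. SAP section 4 reports, for Phase 2, only a slightly greater proportion with worse self-assessed scaling, burning and stinging (mild) than on vehicle, and gives no discontinuation rates by arm. The direction is plausible but not documented.
- A reader might infer that a confirmatory conclusion is at risk. ITT is the primary population, and SAP 8.1.8 confines the gated secondary tests to it.

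**Conclusion.** The inconsistency is real and limited. PP keeps related-AE and lack-of-effect failures who leave the study. It removes those who stop only the product and stay, once the last application is on or before Day 78 for a Day 85 visit. For AEs, the gap concerns mainly non-severe related events.

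Under the stated assumptions PP active IGA success would be overstated by about 0.9 to 2.0 points. That range rests wholly on an assumed rate, an assumed 225 other patients, uniform failure among those affected, and none on vehicle. Similar stops on vehicle would offset it. No primary or gated result changes. This is a minor point, worth making because it takes an outcome-related exclusion out of the supportive analysis at almost no cost.

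**What to change.** Before unblinding:

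1. In SAP 8.4.4 and 8.1.5, change the trigger from discontinuing the study to discontinuing study product or the study, leaving the two qualifying reasons (related AE, documented lack of treatment effect) as they are.
2. State that the compliance, missed-visit and Week 12 attendance and window exclusions do not apply to these patients.
3. In PP, score both groups by the failure value already in 8.1.5. Using observed values for stayers and zero change for leavers would rebuild the unequal handling. Say that, for stayers, this scoring is confined to PP, so that their observed Week 12 values are kept in ITT.
4. As a clarification only, state whether the lack-of-effect phrase includes the worsening row of Table 14.0.1, as the combined reason in protocol 12.2 suggests.
5. Record the departure from protocol 17.1.4 in SAP section 10.

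The cost is SAP text, with no new data. PP results may become slightly less favourable, PP moves a little closer to ITT, and the stayers' observed Week 12 values go unused in PP.
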